Hypothesis 2b. Considering women randomized to MMB who discontinue AD and women randomized to UC who maintain AD, we predict that a treatment selection algorithm will identify which approach works best for whom (baseline characteristic profiles) and that women who receive the algorithm indicated approach will have superior outcomes to those who receive the algorithm contraindicated approach.

Aim 3: To test the extent to which digital MMB engages putative targets.

Hypothesis 3: We predict that women randomized to MMB will show significantly greater improvement in maladaptive cognitive processing (i.e., reduced rumination, increased mindfulness and self-compassion) than women randomized to UC and that these changes will mediate relapse prevention.

UPWARD Supplemental Arms

Objective: In the supplemental arms we will investigate the prevalence, severity, longitudinal course, correlates and predictors of suicidal ideation and behavior among women during pregnancy and the postpartum period (Arm 1a). We will also examine the safety, feasibility, and acceptability of enrolling pregnant women with suicidal ideation in our parent trial of MMB compared to usual care (Arm 2). Additionally, we will describe the resources for responding to suicidal risk that are available for pregnant and postpartum women in community settings and the experiences of healthcare providers who provide care to these women during such a critical time in their lives (Arm 1b). We will lastly use a cross-sectional design to describe the characteristics and correlates of suicidal ideation and behavior among pregnant women (Arm 1c).

Arm 1: We will characterize a real-world population of pregnant and postpartum women by describing the characteristics, correlates, course, and predictors of suicidal ideation and behavior using mixed-methods in the context of cross-sectional and longitudinal designs.

Aim 1a. Using a prospective longitudinal design, we will describe the characteristics, correlates, course, and predictors of suicidal ideation and behavior among pregnant and postpartum women using clinical and qualitative interviews, self-report instruments, behavioral task, and medical records from community providers (n = 125).

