5	Facing Difficulties	Increasing use of mindful attention at the first step in responding effectively to difficulties, including difficult internal experience such as sadness; decreasing judgmental thoughts and avoidant responses to difficulties.
6	Thoughts Are Not Facts	Decreasing affective reactivity to thoughts previously associated with depression; learning to “de-center” from difficult thoughts, recognizing one’s personal patterns of recurring thoughts,
7	Building Your Plan of Action	Identifying unique ‘signatures’ of mood worsening; identifying activities that improve or deteriorate mood; developing action

		plans to implement during periods of high risk; using mindfulness practice explicitly to guide action plan steps.
8	Supporting Your Practice in the World	Emphasizing the importance of regular self-care routines, identifying 'your daily routine of mindfulness practice'; reinforcing links between mindfulness practices, wellbeing and maintenance

MMB for Moms may be a promising intervention for pregnant women with suicidal ideation, as it delivers digitally both the content and structure of in-person MBCT. The standard MMB for Moms program will be implemented for participants in UPWARD Supplemental Arm 2; however, measurement expansion for Supplemental Aim 2 will probe participant responses to the content and the potential need for additional information specific to suicidal ideation and behaviors.

Usual Care (UC). Usual care will not be constrained for any study participants, including those randomized to MMB. The study will not constrain or influence women's decisions about maintenance or discontinuation of AD for all participants. Usual care will be augmented in two ways. First, we will provide ongoing study assessments and the provision of feedback to participants based on their responses to the PHQ-9, EPDS, and clinical interviews (e.g., "Your answers seem to suggest that you are having significant symptoms of depression. We recommend that you talk with your community care provider about whether treatment or modification of treatment might help"). Usual care also will be augmented by ongoing availability of study physicians with perinatal psychiatric expertise in response to queries from community providers regarding changes or reintroduction of pharmacologic treatment during pregnancy or the postpartum period for study participants.

Prospective Follow-up and Community Outreach

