For the analysis of rates of relapse, we will examine time to relapse as rated by the MINI during pregnancy and across the 6-month postpartum follow up using survival analysis. Survival rates will be compared using Cox proportional hazard regression and illustrated in Kaplan-Meier curves (Collett, 1994). However, time to attrition is a competing risk that can be related to time to relapse. We will adopt the subdistribution hazard model (SHM) developed by Fine and Gray to account for the possible non-independence of the censoring mechanism.²⁵

For the continuous outcomes, we will use Hierarchical Linear Models (HLM) as our primary analytic model, which will compare change over time between groups on depressive symptom burden using the PHQ-9. HLM is flexible with respect to the nature of change over time (i.e., linear, piecewise linear, loglinear, etc.), and will accommodate the within subject correlation through the inclusion of random effects at the patient-level, accounting for the patient-to-patient deviations. Pattern-mixture models²⁶ will be used to assess whether important estimates (i.e., intervention effects) are dependent on missing data and to provide overall estimates of effects by averaging over the various missing-data patterns.

Analysis for Specific Aim #2: To explore the specific benefit of MMB relative to AD discontinuation and questions regarding personalization that are of strong interest to pregnant women and their healthcare providers.

H2a: Comparison of MMB to UC among women who discontinue AD: Our analysis will be the same as H1 with both the time-to relapse and continuous outcome models. We predict that rates of relapse and symptom burden among women randomized to MMB who discontinue AD will be significantly superior to those randomized to UC who discontinue AD.

H2b: Treatment Selection Algorithm: We predict that the use of a treatment selection algorithm will differentiate two profiles of women based on pre-treatment characteristics (those who are optimally suited to discontinue AD and engage MMB to minimize their risk of relapse, and those who should continue AD to minimize risk of relapse) and that women who are randomized to the algorithm indicated approach will have significantly lower risk of relapse and symptom burden than women who are randomized to their algorithm contraindicated approach.

Analysis for Specific Aim #3: To test the extent to which digital MMB engages putative targets.

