For the continuous outcomes, using the method described by Ahn et al. to derive formulas for power estimation of linear mixed models,³³ power calculations can be made for repeated measures designs under specified assumptions. Based on a sample size of 300 per group, assuming 30% attrition for a total of 175 per arm randomized, with an alpha-level at 0.05 based on a 2-tailed test, assuming a within correlation of 0.5, we have power of 86.5% to detect an effect size of .25. Varying the effect size, we have 95.7%, 99.0%, and 99.8% power for effect sizes of 0.3, 0.35, and 0.4 respectively, which are much smaller than the d=0.70 effect size

observed in our efficacy study of MBCT with pregnant women,³⁴ indicating that we are sufficiently powered.

Power Analysis for Specific Aim #2: To explore the specific benefit of MMB relative to AD discontinuation and questions regarding personalization that are of strong interest to pregnant women and their healthcare providers.

H2a: Comparison of MMB to UC among women who discontinue AD: Anticipating balance across the 4 cells (randomized to MMB or UC; choice of discontinue AD or maintain AD), with approximately 300 participants across the two cells of interest, we have 82.8% power to detect a 23% difference in relapse rates with 30% attrition, which is smaller than what would be expected comparing the relapse rates among women who received MBCT (19%) in the [name] et al. study of MBCT with pregnant women³² to the rate of relapse among women who discontinued AD during pregnancy (66%) in the Cohen et al. prospective study¹⁰).

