It is possible that participants may experience injury or discomfort when engaging in the mindfulness stretching/yoga practices at home. The mindfulness and yoga practices included in the MMB intervention have been specifically tailored to pregnant and postpartum women. A description of the mindfulness/yoga components will be included in the consent form so that individuals are informed about the nature of the practices, and the digital program will instruct participants not to engage in any exercise or practice they think will be harmful to their health or well-being.

Usual care will not be constrained for any study participants, including those randomized to MMB. Usual care will be augmented by ongoing study assessments and the provision of feedback to participants based on their responses to the PHQ-9, EPDS, and clinical interviews (e.g., “Your answers suggest that you are having significant symptoms of depression. We recommend that you talk with your prenatal care provider about whether treatment might help”). Usual care also will be augmented by ongoing availability of study physicians with perinatal psychiatric expertise for community clinicians treating women with pharmacologic treatment. All treatment decisions, including use of medications and treatment of emergent symptoms, will be managed by the participant’s community prescriber who is not a study investigator. Participants in the UC group will be followed naturally, and no clinical interventions will be made by study investigators. The probability and magnitude of harm or discomfort associated with participation in this arm of the study is not anticipated to be greater than that encountered in daily life.

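### H2b calls its two strategies randomized, but antidepressant use is self-chosen, so the algorithm contrast is observational and lacks adjustment for that choice beyond at most four moderators

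*Combined protocol and SAP*

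**What the plan says.** The H2b analysis text in Section VI predicts that "women who are randomized to the algorithm indicated approach will have significantly lower risk of relapse and symptom burden" than women whose approach the algorithm advises against. Section II, Hypothesis 2b, defines the comparison as "Considering women randomized to MMB who discontinue AD and women randomized to UC who maintain AD" and words the prediction differently: "women who receive the algorithm indicated approach will have superior outcomes".

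On how women come to be in these groups:

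- Section IV (Subject Enrollment) randomizes MMB against usual care (UC) only, 300 per arm, in blocks of four. AD status at randomization is a stratification factor.
- Section V, Usual Care: "The study will not constrain or influence women's decisions about maintenance or discontinuation of AD".
- Section VI, Power Analysis for Specific Aim #2, H2a, describes the four cells as "randomized to MMB or UC; choice of discontinue AD or maintain AD".
- Section VII: "All treatment decisions, including use of medications and treatment of emergent symptoms, will be managed by the participant". That sentence goes on to name her community prescriber, who is outside the study team.

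On the analysis, the H2b power paragraph projects 150 women in each of the two cells, allows up to four moderators, and names PROC QLEARN. Preliminary Analyses adds AD exposure as a covariate, plus any variable that differs between MMB and UC and predicts outcome.

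**The concern.** No woman is randomized to either combined approach: the MMB/UC half is assigned and the AD half is chosen. Women who stop AD may differ in prognosis from women who stay on it, and the H2b cells differ on that choice by definition. A difference between indicated and contraindicated women can then reflect who chose what, even if neither MMB nor AD matters.

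What is at stake is the reading of the output. H2b is meant to yield a rule separating women suited to stopping AD with MMB from women who should continue AD. If the report repeats the word 'randomized', readers will give that rule the credibility of a randomized comparison. Aim 2 is also not incidental to the design, since the Aim 1 power paragraph says that the total of 600 takes account of its needs.

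**Working it through.** **1. The plan's own sizing.** The plan takes 280 women at interval width 0.38 and moves to width 0.40. If N scales with 1/width², 280 × (0.38/0.40)² = 252.7, against 250 stated. Terms: 1 treatment + 4 moderators + 4 interactions = 9. Cells: 0.5 × 300 + 0.5 × 300 = 300. These figures reproduce. The problem is not in the sizing.

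**2. Do the planned adjustments reach the AD choice?**

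- *AD covariate.* Code arm = 1 for MMB and AD = 1 for maintain. In the two H2b cells AD = 1 − arm, so their correlation is −1 and the design (intercept, arm, AD) has rank 2 of 3. A maintain/discontinue covariate cannot be estimated beside arm there. With all four cells, intercept, arm, AD and arm × AD have rank 4 of 4.
- *Covariate screen.* It looks for MMB-versus-UC differences, which randomization should make small. It does not look at differences between the two H2b cells.
- *Stratification.* It balances AD status at entry between arms. It cannot balance two cells defined by opposite AD status.
- *Causal methods under Aim 3* (marginal structural models, principal stratification and others, with sensitivity analyses). They are specified for the mediators, not for H2b.
- *Q-learning model.* It does adjust for the up to four moderators it contains. What remains open is confounding beyond those.

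**3. Crude illustration (all inputs assumed; no true effect of MMB or AD).** Half the women have 20% relapse risk and half 60%; 65% of the low-risk and 35% of the high-risk women stop AD, so half stop overall.

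- Discontinuers: 0.65 × 0.20 + 0.35 × 0.60 = 0.34.
- Maintainers: 0.35 × 0.20 + 0.65 × 0.60 = 0.46. Gap: 12 points.
- Milder inputs (30%/50% risk, 60%/40% stopping): 0.60 × 0.30 + 0.40 × 0.50 = 0.38 against 0.40 × 0.30 + 0.60 × 0.50 = 0.42. Gap: 4 points.

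Swapping the stopping probabilities reverses the sign. Within each risk stratum the gap is zero, so it disappears if that risk factor is among the modelled moderators.

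**4. Illustration of an H2b-type contrast.** This used 1,000 simulated trials, about 150 women per cell, and a 10-fold cross-fitted linear model with four baseline moderators. There was no true effect, and one unmeasured factor drove both AD choice and relapse. A false win is z > 1.96 in favour of the indicated approach.

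| Assumed relapse, maintain / discontinue | False advantage, points | False wins |
|---|---|---|
| 41% / 41% (choice unrelated to prognosis) | −0.5 | 3.7% |
| 45% / 37% | 3.6 | 17% |
| 48% / 34% | 9.8 | 43% |
| 51% / 32% | 17.0 | 79% |

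The same algorithm applied by randomized arm to all 600 gave 0.2 points and 6.4% false wins in every scenario. Both 3.7% and 6.4% exceed the nominal 2.5%, so this simple test is not exactly calibrated. What matters is the rise down the table. The relapse splits are assumptions: the documents give 66% for discontinuers in one cited study and no matching figure for maintainers.

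**The case against.** The other side has four good arguments.

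- *Aim 2 is labelled exploratory, and the plan is open elsewhere about AD being a choice.* Both are true. Section II already uses the right verb, so part of this is one wrong word. Correcting it would not supply the missing adjustment, though, and the hypothesis still predicts a significant difference.
- *The perfect tie between arm and AD status is the question, not an error.* This stands. A reader might infer that H2b is invalid because it cannot separate an MMB effect from an AD effect. The documents do not support that: H2b compares two whole strategies, and such a comparison need not split them. The tie matters here only because it disables the AD covariate. Nor is the rest of the sample lost, since H1 uses both full arms and H2a compares MMB with UC among discontinuers.
- *The 12-point gap is not the H2b bias.* This also stands. It is a crude discontinuer-versus-maintainer difference from invented inputs, before any moderator adjustment. The simulated figures need an unmeasured factor of assumed strength.
- *A four-cell weighted model would be a poor remedy.* Agreed. Separate arm, AD and interaction terms need 1 + 1 + 4 + 4 + 4 = 14 terms, before any arm-by-AD term, against the 9 sized. Women already off AD at randomization could receive extreme weights, because entry status may nearly decide their cell. Weights built on measured variables cannot remove unmeasured confounding.

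**Conclusion.** The point holds in a limited form. Describing the H2b approaches as randomized is wrong and conflicts with Sections II, V and VII and with the plan's own power text. The contrast is observational, and the plan specifies nothing for self-selection into the two cells beyond the moderators in the Q-learning model. This follows from the text and needs no assumed figure.

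The size and direction of any bias cannot be derived from the documents. Either AD group could have the worse prognosis, and the bias could be negligible if the chosen moderators capture the reasons for stopping. The 4- and 12-point gaps and the simulated error rates show only what could happen under stated assumptions.

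A reader might go further and doubt the trial's main result. That is not supported: the Aim 1 comparison of MMB with UC rests on the randomized arms and is untouched.

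**What to change.** 1. In the H2b analysis text, replace 'randomized to' with 'receive', and state that H2b is an observational, hypothesis-generating comparison of two strategies.
2. Define AD status at a fixed time point and count H2b outcomes only after it. As written, no time point is given. Section V has participants with marked symptoms advised to discuss treatment changes with their provider, so AD status read during follow-up could be a consequence of the outcome.
3. Adjust the two-strategy contrast for baseline predictors of AD choice and relapse already collected: prior episodes, baseline PHQ-9, CTQ and the other personalization variables. Use propensity weighting (stabilised or truncated) or covariate adjustment, with overlap checks. Handle women already off AD at randomization separately or in a sensitivity analysis.
4. Add a sensitivity analysis for unmeasured confounding, since step 3 deals only with measured variables.
5. As a supporting analysis, fit the selection model by randomized arm in all 600 women and report it as the randomized evidence on moderators. This keeps the 9 terms already sized. It answers a different question from the two-strategy contrast, so it supports H2b and does not replace it.

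Cost: changes to the analysis text, a little more analysis work, and no new data. Intervals for H2b will be somewhat wider. The plan has 300 − 250 = 50 women to spare before attrition, so the effective sample size after weighting should be reported. The stated conclusion for H2b becomes weaker.

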We propose to address a significant gap in the evidence regarding effective approaches to prevent depressive relapse among women with recurrent depression who maintain euthymia using AD and who wish to conceive or who are pregnant. Relapse rates of depression following AD discontinuation among such women has been established¹⁰, and the efficacy of MBCT in mitigating relapse risk in pregnant women with recurrent depression compared to UC also has been demonstrated¹⁴. But the effectiveness of MBCT has not been tested in a definitive trial; the question of whether MBCT can mitigate risk for depressive relapse among pregnant women on AD, including among those who discontinue AD proximate to or during pregnancy, also has not been addressed. Reproductive age women with recurrent depression and their healthcare providers need to know, first, if a scalable digital non-pharmacologic prevention approach is superior to UC in community settings, and second, whether MBCT can attenuate risk for depressive relapse among those who elect to discontinue maintenance AD treatment proximate to or during pregnancy. Lastly, the capacity to identify which women are most likely to benefit from a non-pharmacologic or pharmacologic approach personalizes the risk benefit decision making process for reproductive age women on AD planning to conceive or who are pregnant.

UPWARD Supplemental Arms (UPWARD-S)

The prevalence of suicidal ideation and behavior among perinatal women has been reported to be 5-14%.³ Precise estimates of suicidal ideation and behavior during pregnancy are still unclear and may vary based on presence of prior psychiatric illness.⁴⁻⁷ Because suicidal ideation and behavior are associated with multiple adverse correlates and consequences among perinatal women, including being among the leading causes of maternal mortality,⁸ it is critical to understand the prevalence, severity, longitudinal course, correlates and predictors of suicidal ideation and behavior among women during pregnancy and the postpartum period.

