In UPWARD, UPWARD Extension and UPWARD-S, if suicidality is endorsed with a score of greater than 1 on EPDS item #10 or PHQ-9 item #9 or on any of the self-report questionnaires (such as the SITBI or CCM), subjects will be prompted to complete the CS-S to assess risk of suicidality. Study subjects will also be given the national suicide [contact]) and informed that answers to online questionnaires are not monitored in real time. A positive score on questions 3, 4, or 5 on the CS-S, indicating intention or plan for suicidality, will prompt a safety call by study physicians. Suicidality expressed during the course of clinical or qualitative interviews, either through discussion, endorsement of the suicidality item on the MINI mood module, endorsement of items 3, 4, or 5 on the suicidality module of the MINI, or via scoring >2 on the MADRS item 10, will prompt study staff to complete the CS-S with the participant. A positive score on items 3, 4, or 5 of the CS-S administered by staff will also prompt a safety call by study physicians. In addition, subjects will be told by study staff to call their community providers and go to their nearest emergency room. Endorsement of items 3-5 on the CS-S prompting a physician safety call has been the threshold used in previous studies at the collaborating site (University of Colorado Boulder). As this is a community-based study with collaboration from community physicians, these providers dictate treatment. We will notify community providers directly via phone or fax within 24 hours from report of positive scores on CS-S items 3-5.

VI. BIOSTATISTICAL ANALYSIS

Preliminary Analyses: Differences between the MMB and UC in demographic characteristics and depression related characteristics (e.g., symptom severity, comorbidity) will be assessed using Chi-square test for binary variables, Cochran Mantel Haenszel tests for categorical variables, and t-tests for continuous variables. Variables that show significant group differences and predict outcome will be entered in analyses as covariates; AD exposure will be included as a covariate. All participants will be considered evaluable for analysis (intent-to-treat sample). Significance levels will be evaluated at $p < .05$, and effect sizes reported.

Analysis for Specific Aim #1: To test the relative risk for depressive relapse and reduction of symptom burden between women randomized to digital MMB or UC.

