H2b: Treatment Selection Algorithm: Although there has been growing interest in trials focused on estimation of an optimal personalized treatment strategy,³⁵ there are no standard formula since the outcome of interest, the personalized treatment regimen, is not a measurable outcome as in typical power derivations.³⁶ Laber and colleagues provide a method for sizing such a trial, which they apply to their fertility (time to pregnancy) data example.³⁷ In their setting, they estimated a sample size of 280 was needed to yield 80% power for superior coverage with 9 terms (including main effects and interaction terms) with an interval width of 0.38. Based on a slight modification of width to 0.40, we estimate a sample size of 250 is needed with 9 terms. Based on our prior data,¹⁰ we project that 50% of participants randomized to MMB will discontinue AD (n=150) and 50% of participants randomized to UC will continue AD (n=150); thus, our randomized sample (N=600) should be sufficiently powered to build a model with up to 4 moderator variables (the number identified in our preliminary data). We will conduct PAI analysis with the SAS software procedure PROC QLEARN.

Power Analysis for Specific Aim #3: To test the extent to which digital MMB engages putative targets. Fritz et al. derived sample size requirements to guarantee 80% power.³⁸ With a small to medium effect for treatment on the mediator and a small to medium effect for treatment on outcome, covarying the mediator, the sample size for 80% power is 224 patients; therefore, our proposed sample, even with as much as 30% attrition is more than sufficient to test mediation with 80% power.

VII.. RISKS AND DISCOMFORTS

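### H2b can report successful treatment selection when one approach is merely better on average, because its only significance criterion compares indicated with contraindicated women

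*Combined protocol and SAP*

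**What the plan says.** Hypothesis 2b (Section II) concerns two groups: women randomized to MMB who stop AD, and women randomized to UC who stay on AD. For these, "we predict that a treatment selection algorithm will identify which approach works best for whom", on the basis of baseline characteristics.

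Section VI, Analysis for Specific Aim #2, H2b, has two limbs. The first is that the algorithm "will differentiate two profiles of women based on pre-treatment characteristics". The second is that "women who are randomized to the algorithm indicated approach will have significantly lower risk of relapse and symptom burden" than women on the contraindicated approach. Only the second limb carries a significance criterion. The Preliminary Analyses paragraph sets the level at .05. Two-sided testing is stated only for the continuous-outcome power under Aim 1 ("with an alpha-level at 0.05 based on a 2-tailed test"), and I assume it for H2b.

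The H2b power paragraph names the Personalized Advantage Index, run in PROC QLEARN, and concludes that the sample "should be sufficiently powered to build a model with up to 4 moderator variables". Its nine terms include interactions, so the relevant terms are in the fitted model. The documents specify no test of those terms, no comparison with one approach for all, no minimum size for either profile and no validation method. Aim 2 is worded as exploratory. Section V (Usual Care) says that the study leaves decisions on AD unconstrained, so AD status is chosen even though H2b speaks of women being randomized to an approach.

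**The concern.** The claim is about effect modification: baseline profile determines which approach is better. The test can reject without any effect modification. If one approach is better for everyone by the same amount, a sound algorithm recommends it to most women. The indicated women are then mostly the better group and the contraindicated women mostly the worse one.

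This is separate from overfitting. Testing the algorithm on women who did not build it removes optimism in the predictions, but it leaves the average difference in the contrast.

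The Background says that "the capacity to identify which women are most likely to benefit from a non-pharmacologic or pharmacologic approach personalizes the risk benefit decision making process". On a false positive, women and providers could be told that a woman's profile bears on whether to stop AD, when the data show only an average difference between two groups that partly selected themselves.

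**Working it through.** **Inputs from the plan.** N = 600, with half of each arm in the relevant AD group: 600 x 0.5 x 0.5 = 150 per cell, 300 in all. Applying the 30% attrition used elsewhere in the power section gives 300 x 0.7 = 210, or 105 per cell. Up to 4 moderators: 1 approach + 4 main effects + 4 interactions = 9 terms.

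**The plan's own figure.** The reference example needs 280 at interval width 0.38. With N proportional to 1/width squared, 280 x (0.38/0.40)^2 = 252.7, against the stated 250. The figure reproduces, but it concerns interval width and coverage. The plan gives no error rate for the indicated-versus-contraindicated test.

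**Expected contrast with no moderation.** Take equal cells and advice unrelated to the approach received. Among indicated women a share q received the better approach; among contraindicated women a share 1 - q did. The expected difference is d[q - (1 - q)] = d(2q-1). For d = 20 points, 50% relapse in the worse approach (assumed) and 105 per group:

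| q | Expected contrast | Chance of significance |
|---|---|---|
| 1.0 | 20 points | 85% |
| 0.9 | 16 points | 66% |
| 0.8 | 12 points | 43% |
| 0.5 | 0 | no inflation |

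**Simulation.** Four standard normal moderators, no interaction, nine-term linear model, 50% relapse in the worse approach (assumed). Entries are the share of trials in which the contrast is significant in favour of indicated women (nominal 2.5%).

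| Uniform difference | 10-fold CV, N=300 | 10-fold CV, N=210 | Independent training set, N=300 | Independent training set, N=210 |
|---|---|---|---|---|
| 0 | 5.2% | 6.2% | 2.4% | 2.3% |
| 10 points | 26% | 19% | 21% | 14% |
| 20 points | 82% | 67% | 86% | 69% |

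The excess at zero difference is absent with an independent training set, so it is a cross-validation artefact and not the mechanism at issue. The formula agrees with the simulation. At N=210 and 20 points the mean q was 0.907, so 20 x (2 x 0.907 - 1) = 16.3 points, against 16.6 simulated.

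Logistic models with average risk near 40% give similar results. The cross-validated range over the assumptions tried is 18 to 27% at 10 points and 62 to 82% at 20 points. For a continuous outcome, a uniform 0.25 SD gives 22 to 37% and 0.4 SD gives 54 to 81%, depending on N and the simulation assumptions. In no-moderation relapse trials, following the algorithm gave 1 to 3 points more relapse than giving everyone the better approach.

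**Adding the two-profiles limb (20 points, four fixed moderators, cross-validated).** Requiring at least one woman in each profile leaves about 58 to 72%. Requiring at least 10% of women in the smaller profile leaves about 7 to 15%. At 10 points and N=210 the same two figures are 18% and 10%. If interactions are kept only at p < 0.10 within each fold, the raw rate at 20 points is 76 to 89%, falling to 41 to 48% and 5 to 6% under the two requirements.

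**Alternative tests on the same question.** With uniform differences of 5 to 23 points, an out-of-sample recommendation-by-approach interaction rejects favourably in 1.0 to 3.2% (nominal 2.5%). The joint 4-df interaction test rejects in 3 to 7% (nominal 5%).

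**The case against.** **H2b has two limbs.** If every woman received the same advice, the first limb would fail on its face. This is the strongest objection, and it limits what can be claimed. A reader might infer that 82% is the false-support rate for H2b as written. The documents do not support that, because the figure ignores the first limb. But that limb has no test and no size threshold, and estimation noise usually leaves a small second profile.

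**The largest differences are not predicted for these cells.** The plan's 20 points is MMB against UC, and its 23 points is MMB against UC among women who stop AD. For MBCT against maintenance AD, the Background reports comparable protection, which points towards zero. This stands: the 20-point figures show the scale of the problem and are not a forecast. Self-selection into AD status could still create a difference.

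**The contrast is not blind to selection.** A reader might infer that its null is simply equal outcomes overall. It is not: with real moderation and no overall difference it rejected in 53 to 88% of simulated trials at 150 per cell. The fault is that it mixes the average difference with selection, and the inflation vanishes at a 50:50 split of advice.

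**Aim 2 is exploratory.** This lowers the priority, but H2b still predicts a significant result and attaches a personalization claim to it.

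**An interaction test alone is not enough.** This also stands. In one simulated case where one approach was better for every woman but by varying amounts (mean 0.5 SD, slope 0.28), the joint test rejected in 61% (N=300) and 43% (N=210). Picking the best four of the eleven listed personalization measures on the same data gave 34% false rejection.

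**Conclusion.** The concern holds in limited form. As worded, H2b's significance criterion can be met by a uniform difference between approaches, and out-of-sample testing does not cure this. With no moderation, cross-validated favourable rejection against a nominal 2.5% is about 5% at zero difference, 18 to 27% at 10 points and 62 to 82% at 20 points. How far the two-profiles limb reduces this depends on a threshold that the plan does not set.

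These figures rest on assumed relapse risks of around 40 to 50%, normally distributed moderators, relapse treated as binary without censoring, and a two-sided .05 test. The true difference between the cells is unknown, so the documents do not show that a false personalization result is likely, only that the stated rule would not guard against one. This is worth correcting within an exploratory aim; it does not touch Aim 1.

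**What to change.** Amend the H2b text under Analysis for Specific Aim #2 so that the personalization claim requires both of the following:

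- **Interaction.** Either a test of approach-by-moderator interaction, with the up to 4 moderators fixed in advance or selected inside the cross-validation, or an out-of-sample recommendation-by-approach interaction.
- **Gain over one approach for all.** The out-of-sample difference in relapse and PHQ-9 between following the algorithm and giving everyone the single better approach, with a confidence interval. This must be part of the criterion, because an interaction alone can arise when one approach is better for every woman.

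Report the size of each recommended profile and the approach difference within it. Keep indicated versus contraindicated as a descriptive contrast. State that AD status is chosen, so these contrasts and interactions remain open to confounding; the change does not remove that.

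**Cost.** Some wording and a few lines of code, with no new data or participants. A uniform advantage would no longer count as success for H2b. Power under real moderation may move either way. At 150 per cell, the joint interaction test had 73% against 53% for the current contrast in one scenario and 98% against 88% in another. In a different scenario, the recommendation-by-approach test had 60% against 66% (N=300) and 40% against 46% (N=210).
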